## 7.2. Participant Discontinuation/Withdrawal from the Study

Discontinuation is expected to be uncommon.

A participant may withdraw from the study:

- at any time at the participant's own request
- at the request of the participant's designee (for example, parents or legal guardian)
- a participant will be withdrawn from the study in case of inadvertent enrollment
- at the discretion of the investigator for safety, behavioral, compliance, or administrative reasons
  - If the participant becomes pregnant during the study (see Section [8.3.2](#) for additional details)
- if enrolled in any other clinical study involving an investigational product, or enrolled in any other type of medical research judged not to be scientifically or medically compatible with this study
- if the participant, for any reason, requires treatment with a therapeutic agent that is prohibited by the protocol and has been demonstrated to be effective for treatment of the study indication. In this case, discontinuation from the study occurs prior to introduction of the new agent.

At the time of discontinuing from the study, if possible, the participant will complete procedures for an ED visit and post-treatment follow-up, if applicable, as shown in the SoA. If the participant has not already discontinued the study intervention, the participant will be permanently discontinued from the study intervention at the time of the decision to discontinue the study.

If the participant withdraws consent for disclosure of future information, the sponsor may retain and continue to use any data collected before such a withdrawal of consent. If a participant withdraws from the study, the participant may request destruction of any samples taken and not tested, and the investigator must document this in the site study records.

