Missing values for the primary and multiplicity adjusted endpoints at Week 52 and at Week 48 for SBP will be handled as follows. For efficacy analysis relative to the "efficacy" estimand, no explicit imputation will be performed. For efficacy analysis relative to the "treatment regimen" estimand, missing values will be imputed using multiple imputation based on the reason of intercurrent events. The statistical inference over multiple imputations will be guided by the method proposed by Rubin (1987). The intercurrent events and the resulting missing values will be handled as follows:

Intercurrent events	Strategy to handle intercurrent events	Assumptions for missing values	Methods to handle missing values
---------------------	--	--------------------------------	----------------------------------

Study DC due to the COVID-19 pandemic (after other reasons for missing data are ruled out) or incorrect study procedure leading to invalid measurements ascertained while on treatment	Hypothetical	MAR	Use observed data without any imputation
All other study discontinuations	Treatment policy	MNAR	Multiple imputation. Details will be indicated in SAP

Abbreviations: COVID-19 = coronavirus disease-2019; DC = discontinuation; MAR = missing at random;

MNAR = missing not at random.

Handling of missing, unused, and spurious data are addressed prospectively in the overall statistical methods described in the protocol and in the SAP, where appropriate. Adjustments to the planned analyses are described in the final CSR.

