| | | 
Section 4.1:
 
 Added language on baseline AHI. Modified the postbaseline definition for PRO measures. Updated that geographic region will be used in lieu of pooled country as a covariate in analysis models. Changed AHI groups to be included in the model as covariates. | 
 Language added for clarification. Updated to clarify the definition. Changed to reduce the number of strata in the model and to keep enough participants in each covariate strata. Changed the group category from “moderate” to “not severe” to incorporate inadvertently enrolled participants. |

| SAP Version | Approval Date | Change | Rationale |
|-------------|---------------|---|---|
| | | 
Section 4.1.2:
 
 Updated missing data and imputation method in Table GPIF.4.2. | 
 Missing data imputation algorithm revised, in part to include inadvertent enrollees in analysis, and language on missing data clarified per FDA feedback. |
| | | 
Section 4.1.2:
 
 Added no OSA and mild categories to baseline OSA category | 
 Added to account for inadvertently enrolled patients |
| | | 
Section 4.1.6:
 
 Added definition for baseline and postbaseline concomitant medication use. | 
 Clarified definition for related tables and listings. |
| | | 
Section 4.2:
 
 Added definition for participant study disposition. | 
 Clarified the definition of participant study disposition based on collected CRF data. |
| | | 
Section 4.4.1.2:
 
 Added analysis for change in log hypoxic burden. Added reporting of unconditional risk difference from logistic regression. | 
 Log scale is deemed appropriate for analysis as the measure is an area under the curve. Added to provide additional measure of treatment effect in accordance to FDA guidance. |

| SAP Version | Approval Date | Change | Rationale |
|-------------|---------------|---|--|
| | | Section 4.6: 
 Added hepatobiliary events, malignancies, and abuse potential as special safety topics. | 
 Updated to provide information on special safety topics. |

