| To demonstrate that tirzepatide at the MTD (10 mg or 15 mg) QW is superior to placebo for Change in exploratory PROs | From baseline to Week 52 Change in EQ-5D-5L utility index EQ-VAS scores Percent of participants with improved categorical shift in: PGIC-OSA Sleepiness PGIC-OSA Fatigue PGIC-OSA Sleep quality PGIC-OSA Snoring |
| To evaluate the effect of tirzepatide on sleep parameters as measured by Actigraphy (AX6) | Change from baseline to endpoint assessment in Daytime sleep duration Daily step counts Average acceleration |

Abbreviations: AHI = Apnea-Hypopnea Index; AX6 = Axivity 6; BP = blood pressure; DBP = diastolic blood pressure; ESS = Epworth Sleepiness Scale; EQ-5D-5L = EuroQol-5 Dimension-5-Level; EQ-VAS = EuroQol Visual Analogue Scale; FOSQ = Functional Outcomes of Sleep Questionnaire; HDL = high-density lipoprotein; hsCRP = high-sensitivity C-reactive protein; MTD = maximum tolerated dose; OSA = obstructive sleep apnea; PAP = positive airway pressure; PGIC-OSA = Patient Global Impression of Change – Obstructive Sleep Apnea; PGIS-OSA = Patient Global Impression of Status – Obstructive Sleep Apnea; PRO = patient-reported outcome; PROMIS = Patient-Reported Outcomes Measurement Information System; QW = once weekly; SASHB = sleep apnea-specific hypoxic burden; SBP = systolic blood pressure; SF-36v2 = Short-Form 36 version 2.

^a Subject to submission wide type 1 error rate control (Vandemeulebroecke et al. 2024).

b BP will be assessed at Week 48 because PAP withdrawal at Week 52 may confound BP assessment.

1.1.1. *Estimands*

Primary estimands

The primary and each key secondary efficacy analysis will be guided by the “*treatment regimen*” estimand and the “*efficacy*” estimand to support global regulatory submissions and publications. The “*efficacy*” estimand provides an on-treatment assessment of efficacy without confounding the treatment effect from the data collected after treatment discontinuation. It represents on-treatment efficacy. The “*treatment regimen*” estimand estimates the treatment effect, including the effect of intervention discontinuation to reflect clinical practice. It represents the efficacy irrespective of adherence to study intervention. The “*treatment regimen*” estimand will be used as the primary estimand to support a marketing application for the FDA.

Efficacy estimand

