- *Handling of intercurrent events*: No intercurrent events since treatment adherence and the initiation of PAP therapy are part of the treatment condition. Methods to handle missing data are described in detail in Section 4.1.2.
- *Rationale*: The treatment regimen estimand estimates treatment effect, including the effect of intervention discontinuation to reflect clinical practice. It is used for submission and registration purpose with regulatory agencies.

Efficacy and treatment regimen estimands will be evaluated for key secondary objectives similarly to the primary objectives.

Safety estimand

The clinical interest for safety estimands is the safety assessment of individual treatment arms up to the end of safety follow-up or study discontinuation in participants with obesity and OSA, from all randomly assigned participants who are exposed to at least 1 dose of study intervention, regardless of adherence to study intervention.

Safety estimand attributes

- *Population*: Adult participants with obesity and OSA who received at least 1 dose of study treatment.
- *Treatment condition*: On- or off-randomized-treatment.
- *Endpoints*: Endpoints corresponding to the safety analyses described in Section 4.6.
- *Population level summary*: Population level summaries will be conducted using the safety analysis set described in Section 3.
- *Intercurrent events*: Potential intercurrent events may lead to study discontinuation or missing data due to a technical or scheduling issue, but there are no planned approaches for accommodating intercurrent events.

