4.1.2. Handling of Dropouts or Missing Data

For the primary and key secondary efficacy endpoint analyses aligned to the treatment regimen estimand and subject to Type 1 error rate control, missing data will be imputed based on the reason for the missing values, as described in [Table GPIF.4.2](#). For analyses aligned to the “efficacy” estimand, missing data will be considered missing at random and hence no explicit imputation will be performed.

For exploratory endpoints and safety analyses, missing values will not be explicitly imputed unless specified otherwise.

For analyses aligned to the treatment regimen estimand, the statistical inference over multiple imputations will be guided by the method proposed by Rubin (1987). The missing values will be handled as follows:

Table GPIF.4.2. Imputation Approaches to Handle Missing/Invalid Data for Treatment Regimen Estimand

| Missing/Invalid Data | Strategy to Handle Missing/Invalid Data | Assumptions for Missing Values | Methods to Handle Missing Values |
|--|---|--------------------------------|--|
| Data missing at baseline, invalid data collected or missing data after treatment DC due to the COVID-19 pandemic (after other reasons for missing data are ruled out), technical issues (that is, sensor error on PSG) leading to invalid measurements ascertained while on treatment, or missing data after study DC due to inadvertent enrollment. | Hypothetical | MAR | Multiple imputation assuming MAR |
| Missing data due to any other reason (for example, study DC due to any reason other than COVID-19 or inadvertent enrollment). | Treatment policy | MNAR | Retrieved dropout imputation ^a . If there are not enough retrieved dropouts to provide a reliable imputation model, placebo-based multiple imputation will be used. |

Abbreviations: COVID-19 = coronavirus disease-2019; DC = discontinuation; MAR = missing at random;

MNAR = missing not at random; PSG = polysomnography; SBP = systolic blood pressure.

^a Retrieved dropout imputation utilizes observed data from participants in the same treatment group who had outcome measures at Week 52 (or Week 48 for SBP) after early DC of study drug to impute the missing value.

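### The catch-all row of SAP Table GPIF.4.2 imputes participants who never stopped study drug as if they had stopped it, or as placebo

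*SAP*

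**What the plan says.** SAP 4.1.2 imputes missing primary and key secondary values for the treatment regimen estimand according to the reason they are missing. Table GPIF.4.2 has two rows.

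- **Row 1 (MAR multiple imputation)** is a closed list: missing baseline, COVID-19, inadvertent enrollment, and "technical issues (that is, sensor error on PSG) leading to invalid measurements ascertained while on treatment".
- **Row 2 (MNAR)** takes everything else: "Missing data due to any other reason (for example, study DC due to any reason other than COVID-19 or inadvertent enrollment"). Study discontinuation is only its example. Footnote a defines the donors as "participants in the same treatment group who had outcome measures at Week 52 (or Week 48 for SBP) after early DC of study drug". If there are too few of them, placebo-based imputation replaces this method.

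The MNAR row in Protocol 9.3.1 is narrower: "All other study discontinuations". Under Protocol 7.2, when someone leaves the study, "the participant will be permanently discontinued from the study intervention at the time of the decision to discontinue the study". The SAP version history describes the change as "Missing data imputation algorithm revised, in part to include inadvertent enrollees in analysis, and language on missing data clarified per FDA feedback".

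SAP 1.1.1 says the treatment regimen estimand "will be used as the primary estimand to support a marketing application for the FDA", and describes its intercurrent events as follows: "No intercurrent events since treatment adherence and the initiation of PAP therapy are part of the treatment condition".

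For ISA2, SAP 4.3.3 and 4.4.1.2 (percent change in AHI) set aside sleep studies done after less than 5 days without PAP, and send the censored post-baseline values back to 4.1.2 for imputation.

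**The concern.** Row 2 sets no condition on drug status, yet both of its methods produce off-drug or placebo values. Since the estimand counts actual adherence as part of the treatment condition, the value to predict for someone who never stopped drug is the outcome without discontinuation. Row 2 predicts a different quantity for that person.

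The documents show how such cases can arise:

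- SBP is taken at Visit 10, which has a window of only ±3 days. A participant can miss that visit and still attend Week 52 on drug.
- Row 1 ties its technical item to the sleep-study sensor, so a lost hsCRP sample falls outside it.
- One missing ESS item invalidates the ESS total (SAP 4.7.2.3). The remission endpoint is then undetermined for a participant with AHI 5-14.

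What is at stake is the accuracy of the estimate that is primary for the FDA application. In ISA2, the table also leaves unclear which row takes the PAP-censored values. If they are read as row 2, an analysis meant to isolate the effect of PAP washout also carries an off-drug penalty. The efficacy-estimand MMRM is not affected.

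**Working it through.** **1. Who falls into row 2 while on drug.** Row 1 reaches a participant still on drug mainly through missing baseline data and technical faults. A value that was simply never obtained is in neither group, so it goes to row 2. SAP 4.3.2, 4.3.3, 4.4.1.2 and 4.4.3.1 all refer back to 4.1.2, so no other section catches the case. For people who leave the study there is no conflict, because leaving ends study drug.

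**2. The plan's own figure.** SAP 5 gives 103 per arm, a 50-point difference in percent change in AHI, SD 50, 25% dropout and two-sided 0.05. With 103 × 0.75 ≈ 77 per arm, the standardized difference is 50 / (50 × √(2/77)) = 6.20, and power is Φ(6.20 − 1.96) > 0.9999. The stated power of at least 90% therefore holds. The smallest difference with 90% power at 77 per arm is 26.1 points.

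**3. Size of the loss.** Let f be the fraction of the tirzepatide arm that has not discontinued but lacks the endpoint, and k the share of the on-drug effect that donors keep. Then

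relative loss = f × (1 − k), and loss in points = f × (1 − k) × 50.

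The relative form applies on any mean-difference scale, including the primary endpoint in events per hour, for which neither document gives a planning figure. Both f and k are assumptions. The placebo fallback sets k = 0 by construction.

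- f = 1%: 0.25 points (k = 0.5) to 0.5 (k = 0)
- f = 2%: 0.5 to 1
- f = 5%: 1.25 to 2.5
- f = 10%: 2.5 to 5
- any f with k = 1: no loss

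**4. Simulation.** The setting was 103 per arm, on-drug effect 50, SD 50 and baseline correlation 0.5. Per arm, 15 participants were off drug and missing and 10 off drug and retrieved (an assumed split of the planned 25%), with 1, 2, 5 or 10 on drug and missing. Each of 2,404 runs per case used 20 imputations on baseline, ANCOVA and Rubin's rules. Loss is row 2 against a row split by drug status on the same data (Monte Carlo SE at most 0.06). The formula columns use f = number/103.

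| On drug, missing | k = 0: formula / simulated | k = 0.5: formula / simulated | Placebo fallback, simulated | Power, row 2, k = 0 |
|---|---|---|---|---|
| 1 | 0.49 / 0.47 | 0.24 / 0.19 | 0.46 | 99.5% |
| 2 | 0.97 / 0.95 | 0.49 / 0.43 | 0.97 | 99.2% |
| 5 | 2.43 / 2.42 | 1.21 / 1.17 | 2.43 | 98.6% |
| 10 | 4.85 / 4.81 | 2.43 / 2.39 | 4.90 | 91.8% |

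With the split row, power was at least 99.6% and the estimate was within 0.11 of the full-data result (SE 0.09). With no drug effect, rejection was 1.0-3.8% under every option. Repeat simulations of the worst case gave power of about 94% and 95% rather than 92%.

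**5. ISA2.** The documents give no censoring rate, so no figure is possible.

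**The case against.** The strongest reply is that row 2 is openly labelled MNAR and is a deliberately conservative default for values with no accepted benign explanation. It errs toward no effect, and it is biased only if the affected participants resemble others who stayed on drug, which cannot be tested. The simulation favours the split because on-drug MAR was built into it. This stands as a caution about the alternative. It does not make an off-drug donor a suitable predictor for someone known not to have stopped.

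Other points carry weight:

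- **Frequency.** Nothing supports 5-10%. The ±14-day sleep-study window makes missed AHI values uncommon, and people who stop attending usually become study discontinuations, where row 2 fits. Conditioning on Week 20 AHI could shrink the shift further, but the SAP does not state the imputation covariates.
- **Worst-case power.** The drop at 10% missing mostly reflects a model fitted to 10 donors. In a 400-run repeat the placebo fallback gave about 99.5%, with the same shift in the estimate.
- **ISA2.** The MAR row in Protocol 9.3.1 covers invalid on-treatment measurements caused by incorrect procedure, and row 1 of the SAP table is the only row that mentions invalid values. Row 1 is arguably the closer fit, but its sensor-error wording leaves this open.
- **Version history.** A change log need not justify each choice of donor, so its silence is not a defect in itself.

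None of these supplies a rule for values never obtained from participants still on drug.

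**Conclusion.** The concern holds. Read as written, row 2 imputes a participant who has not discontinued drug as a discontinuer or as placebo, which does not match an estimand that takes adherence as it occurred. If off-drug outcomes are worse, the treatment effect is understated by f × (1 − k). That is 0.5-2% of the effect when 1-2% of the arm is affected, and 2.5-10% at 5-10%, with donors assumed to keep none to half of the effect. The lower range is the more plausible. This does not inflate type I error or threaten the planned power for AHI. It is a should-fix point about the accuracy of the FDA-primary estimate and about unambiguous pre-specification.

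**What to change.** Split row 2 of Table GPIF.4.2 by recorded study-drug disposition, which SAP 4.2 already collects:

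- **(a) Not permanently discontinued from study drug before the scheduled endpoint visit** (Week 52; Week 48 for SBP): multiple imputation under MAR from same-arm participants who likewise had not discontinued, using baseline and interim values. Completers and temporary interruptions count as not discontinued.
- **(b) Missing after permanent drug discontinuation, including study discontinuation:** retrieved-dropout or placebo-based imputation, as now.

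Do not borrow the last-dose-plus-7-days rule of the efficacy analysis set as the on-drug test. With weekly dosing from day 0, the 52nd dose falls on day 51 × 7 = 357, and 357 + 7 = 364 = 52 × 7 is exactly Week 52. One early or skipped final dose would misclassify a completer.

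State in SAP 4.3.3 and 4.4.1.2 that post-baseline values censored for PAP withdrawal of less than 5 days, in participants who had not discontinued drug, are imputed as in (a).

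The cost is SAP wording and one derived flag. The imputation becomes slightly less conservative for a small subset and rests on an untestable MAR assumption. That assumption is weakest for someone in a long interruption or repeating escalation, whose donors would mostly be uninterrupted. The optional two-way tipping-point analysis can probe it, but only for the primary endpoint.

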4.1.3. Multicenter Studies

Randomization will be stratified by country, and geographic region (US/OUS) will be used as a covariate.

4.1.4. Historical Illnesses and Preexisting Conditions

The count and percentages of participants with historical illnesses and preexisting conditions will be summarized by treatment group using the MedDRA PTs nested within SOC. The SOC will be in alphabetical order. Conditions (that is, PTs) will be ordered by decreasing frequency in the tirzepatide MTD arm within the SOC. This will be summarized for all randomized participants.

4.1.5. Participant Characteristics

A listing of participant demographics for all randomized participants will be provided. The demographic and baseline clinical characteristics will also be summarized by study treatment for all randomized participants. Baseline demographic and clinical characteristics of special interest include but are not limited to:

- age (years)
- sex (female, male)
- race
- ethnicity
- height (cm)
- weight (kg)
- BMI (kg/m²)
- waist circumference (cm)
- age group (<50, ≥50)
- BMI group (<35, ≥35 and <40, ≥40 kg/m²)
- OSA severity (none [AHI <5], mild [AHI ≥5 and AHI <15], moderate [AHI ≥15 and AHI <30], or severe [AHI ≥30])
- geographic region (US/OUS), and
- country.

4.1.6. Concomitant Therapy

Concomitant medication will be summarized by treatment groups and displayed by decreasing frequency of WHODrug PTs in tirzepatide MTD arm. Baseline use of concomitant medication is defined as any medication started prior to the treatment start date and continuing on or after the treatment start date. Postbaseline concomitant medications are defined as those that are being taken any time during the postbaseline period.

In addition, medications of interest (as defined below) will be summarized by treatment groups:

- baseline use of:
 - lipid lowering therapy, by type/class and
 - antihypertensive therapy, by type/class

- Utilization after randomization of
 - antihyperglycemic medication for the treatment of diabetes for participants who develop type 2 diabetes mellitus during the study
 - antidiarrheal medication, and
 - antiemetic medication.

In addition, for ISA2 participants only, a summary of PAP machine use at baseline and postbaseline PAP machine adherence will be provided. Further details are provided in Section 4.7.1. For ISA1 participants, a listing will be provided summarizing any participants who use a PAP machine during the course of the trial.

4.1.7. Treatment Exposure and Compliance

4.1.7.1. Study and Study Treatment Exposure

Summary of duration of follow-up (defined as time in days from date of randomization to the date of the last study visit) will be provided by treatment group in the mITT population.

Summary of duration on study treatment (defined as time in days from date of first dose of study treatment to date of last dose of study treatment plus 7 days) will be provided by treatment group in the safety analysis set.

For the summary of duration on study treatment, the frequency and percentage of participants falling into the following categorical ranges will also be summarized by planned treatment group as well: >0 week, ≥4 weeks, ≥8 weeks, ≥12 weeks, ≥16 weeks, ≥20 weeks, ≥24 weeks, ≥36 weeks, ≥48 weeks, and ≥52 weeks.

No p-values will be reported in these summaries as they are intended to describe the study populations rather than test hypotheses.

